## 8.2. Protocol Deviations

This study will be conducted as described in the protocol, except for an emergency situation in which the protection, safety, and well-being of the patient require immediate intervention, based on the judgment of the investigator (or a responsible, appropriately trained professional designated by the investigator). The Investigator must notify the Sponsor of any deviation from the Investigational Plan. The Investigator should also notify the IRB / EC as required per their local requirements or as directed by the Sponsor. This notice must occur as soon as possible, but in no case longer than five (5) working days after the Investigator becomes aware of a major deviation. Major deviations include, but is not limited to, those that involve the informed consent process, the inclusion/exclusion criteria of the study, SAE/MAE reporting, device misuse or device accountability discrepancies, or any deviation that involves or leads to a serious adverse event in a study participant. Protocol deviations will be reported in tabular form (number of deviations and number of subjects with deviations) as well detailed in a listing.

## 9. STATISTICAL METHODS

### 9.1. Determination of Sample Size

Using Percutaneous Transluminal Angioplasty (PTA) data from a series of clinical studies, VIVA Physicians Inc., developed performance goals that may be used as standards of comparison for safety and effectiveness in the treatment of claudication associated with femoropopliteal disease. The safety and effectiveness of the BioMimics 3D stent will be compared to the VIVA Physicians' defined objective performance goals (OPGs).[4]

- VIVA Physicians' primary safety endpoint is freedom from major adverse events (MAE), defined as all-cause death, index limb amputation and target lesion revascularization (TLR), through 30 days. The lower limit of the one-sided 95% confidence interval of the true femoropopliteal PTA rate for freedom from MAE was 88%, which was established as the primary safety OPG.
- The VIVA Physicians Inc. primary effectiveness endpoint is the primary stent patency rate at 12 months, where patency is defined as freedom from more than 50% restenosis based on DUS peak systolic velocity ratio (PSVR) comparing data within the treated segment to the proximal normal arterial segment. A PSVR > 2.0 is indicative of the loss of patency. The primary effectiveness OPG of 66% was established as two times the observed PTA freedom from loss of patency rate of 33%.

Sample size estimation for the MIMICS-2 Study was performed using VIVA OPGs and outcomes from the Mimics Study, a first-in-man study of the safety and effectiveness of the BioMimics 3D

Stent System conducted at eight investigational sites in Germany in which patients were followed for 24 months after the index procedure.

There are two primary endpoints in the MIMICS-2 Study, one safety and one effectiveness. In order for the trial to be considered successful, both primary endpoint hypotheses must be satisfied, thus no adjustment for alpha is necessary. The size of the study will be driven by the primary effectiveness endpoint as detailed below. Initially, powers of 95% and 85% are considered for primary safety and effectiveness, respectively, in order to preserve an overall power greater than 80%.

#### *Primary Safety Endpoint and Hypothesis Test*

The primary safety endpoint in the MIMICS-2 Study is a composite of Major Adverse Events (MAE) including all-cause death, major amputation performed on the target limb, or CDTLR through 30 days.

The primary safety objective is to demonstrate that the freedom from MAE rate for treatment with the BioMimics 3D Stent System meets the VIVA OPG of 88%. The null and alternative hypotheses are as follows:

H0:  $\pi \leq 88\%$

HA:  $\pi > 88\%$

where  $\pi$  is the population proportion of subjects treated with BioMimics 3D who are free from MAE through 30 days. Hypothesis testing will be conducted using the confidence interval approach. Success on the primary safety objective will be established if the one-sided lower 97.5% Agresti-Coull confidence limit [5] for the proportion of subjects treated with BioMimics 3D who are free from an MAE through 30 days is greater than 88%.

#### *Sample size implications for Primary Safety Objective*

The sample size for the primary safety objective was determined using the method presented in Agresti-Coull [5]. The freedom from MAE rate in the Mimics Study was 100% at 30 days, so a conservative estimate of 98% freedom from MAE in the MIMICS-2 Study was used for sample size calculations.

The following assumptions were used for sample size:

- 95% statistical power.
- Confidence interval approach to hypothesis testing with one-sided 97.5% lower Agresti-Coull confidence limit (one-sided type-I error rate of 2.5%).
- VIVA freedom from MAE OPG of 88%.
- Estimated 98% freedom from MAE in MIMICS-2.

The conclusion was that 83 evaluable subjects would be required to statistically power the primary safety endpoint at the 95% level.

#### *Primary Efficacy Endpoint and Hypothesis Test*

The primary effectiveness endpoint in the MIMICS-2 Study is primary stent patency rate at 12 months. Patency is defined as no significant reduction in luminal diameter (i.e., < 50% diameter stenosis) since the index procedure. Luminal diameter is assessed by core lab using angiography

or duplex ultrasound imaging. Loss of primary stent patency is deemed when peak systolic velocity ratio (PSVR) is  $> 2.0$ , or where angiography reveals  $>50\%$  diameter stenosis, or where the subject undergoes clinically-driven TLR. When both imaging modalities are available, angiography takes precedence.

The primary effectiveness objective is to demonstrate that the 12-month primary stent patency rate after use of the BioMimics 3D Stent System is statistically superior to the VIVA OPG of 66%. The null and alternative hypotheses are as follows:

$$H_0: \pi \leq 66\%$$

$$H_A: \pi > 66\%$$

where  $\pi$  is the population BioMimics 3D patency at 12 months. Hypothesis testing will be conducted using the confidence interval approach. Success in the primary effectiveness objective will be established if the one-sided lower 97.5% Agresti-Coull confidence limit for the proportion of subjects treated with BioMimics 3D that continue to have treated segment patency through 12 months is greater than 66%.

#### *Sample size implications for Primary Efficacy Objective*

The sample size for the primary effectiveness objective was determined using the method presented in Agresti-Coull. The 12-month patency rate for those subjects who received BioMimics 3D stents in the randomized portion of the MIMICS Study was 75% (PSVR  $\leq 2.0$ ) with no CDTLR in the interim, and this value was used as the estimate of BioMimics 3D performance in the MIMICS-2 Study.

The following assumptions were used for the primary effectiveness objective sample size calculation:

- 85% statistical power.
- Confidence interval approach to hypothesis testing with one-sided 97.5% lower Agresti-Coull confidence limit (one-sided type-I error rate of 2.5%).
- VIVA 12-month patency OPG of 66%.
- Estimated 12-month primary stent patency rate in the MIMICS-2 Study of 75%.

The conclusion was that 230 evaluable subjects would be required to statistically power the primary effectiveness endpoint at the 85% level.

### *Final sample size determination*

In order to statistically power both of the primary endpoints simultaneously, 230 evaluable subjects at 12 months are required. It was initially determined that in order to allow for attrition, a sample size of 280 subjects should be enrolled in the MIMICS-2 Study; however, enrollment was stopped at 271 subjects with the expectation that greater than 230 subjects will be evaluable at 12 months based on current drop-out rates and updated estimates of availability of diagnostic DUS images. The power for the primary safety endpoint is actually >99%, keeping the overall study power at approximately 85%.

## **9.2. General Considerations**

### 9.2.1. General Methods

All descriptive statistical analyses will be performed using SAS Version 9.4 or higher [2,3], unless otherwise noted. Derived variables will be independently verified by an independent programmer/statistician. The program review also will include a check whether analyses conform to specifications of the Statistical Analysis Plan. All output will be incorporated into Microsoft Excel or Word files, and formatted as to the appropriate page size(s).

For categorical variables, the number and percentage within each category of the parameter will be calculated. For continuous variables, the N, median, IQR, mean, standard deviation, minimum and maximum values will be presented.

For each parameter, the baseline value will be defined as the last non-missing value collected at the time closest to but before the start of study drug/device administration.

All statistical tests will be performed at the two-sided, 0.05 significance level, unless otherwise noted. Listings of patient data will be created for all study parameters.

### 9.2.2. Adjustments for Covariates

No adjustments for covariates are planned.

### 9.2.3. Handling of Dropouts or Missing Data

For all primary, secondary and exploratory analyses, no imputation of missing data is planned. Subjects who have ascertainment of status at a later out-of-window date (for example, subjects who are known to be free of MAE past 30 days but missed the 30 day visit) are not considered missing as their status is known and their data will be used as noted previously. A sensitivity analysis, specifically a tipping point analysis, will be used to assess the impact of missing data on the study conclusions for the primary endpoints. This sensitivity analysis will be performed on the ITT analysis set.

### 9.2.4. Interim Analyses and Data Monitoring

There is no interim analysis planned with the purpose of altering the Protocol or planned statistical analyses. When all data have been collected and imaging completed for the co-primary endpoints (through 12 months), the database will be cleaned and the primary study analysis conducted. All data available at that time will be summarized for reporting and regulatory filing purposes (PMA submission on primary data set). Additional analyses will be conducted for annual reporting purposes and when all data have been collected for the 24 and 36 month visits.

### 9.2.5. Multicenter Studies

Poolability of study subjects across investigational sites will be explored by comparing the primary outcome measure across sites. Initially, testing of the primary outcomes will be conducted across site at a two-sided  $\alpha=0.15$  level using a chi-square test, unadjusted for covariates. If differences between sites exist at the  $\alpha=0.15$  level, further analysis will compare prognostic factors, protocol violations and study outcomes across sites using a chi-square test for categorical data and t-test for continuous data. For these analyses, any sites with fewer than 10 subjects will be pooled by country. Within the US, sites will be pooled by region (Northeast, Southeast, Midwest and West). If a country/region has fewer than 10 subjects, that country/region will be pooled with its nearest neighboring country/region. Regardless of these findings, if differences between sites exist at the  $\alpha=0.15$  level, summary statistics will be presented for each site. Any differences by study site will be discussed in the study report. If substantial differences emerge, a sensitivity analysis of the primary outcomes may be performed by excluding outlying sites from the analysis.

Additionally, an analysis by region (US vs. OUS) will be conducted for the primary endpoints. Heterogeneity of region will be tested via a chi-square test. If no statistically significant difference exists for the primary endpoints at  $\alpha=0.15$ , the data will be considered poolable by region. If a statistically significant difference exists for the primary endpoints at  $\alpha=0.15$ , the primary endpoints will be presented by region along with 95% confidence intervals. If difference between region exist but can be explained by baseline covariates, then the data will be considered poolable by region, however, descriptive statistics will be presented by region as noted above and discussed in the study report.

### 9.2.6. Multiple Comparisons/Multiplicity

There are two independent primary endpoints in this study. Both endpoints must be met in order to declare study success, thus no adjustment to  $\alpha$  is necessary to account for multiple endpoints.

### 9.2.7. Examination of Subgroups

Heterogeneity of the primary endpoints will also be explored for the subgroup sex (Male vs. Female). Outcomes will be reported separately for each group along with 95% confidence intervals. A chi-square test will be conducted to determine if a statistically significant difference (at  $\alpha=0.15$ ) exists between the groups. If no statistically significant difference exists, then the results will be considered poolable by sex. If differences between sexes exist but can be explained by baseline covariates, then the data will be considered poolable by sex, however, descriptive statistics will be presented by sex as noted above and discussed in the study report.

Primary endpoints will be additionally reported separately for the following subgroups:

- subjects who are taking cilostazol (vs. not taking cilostazol),
- Japan versus rest of world (ROW) and versus the overall study cohort,
- Japan versus US versus Germany,
- subjects implanted with a 5mm stent diameter versus >5mm stent diameter.

In addition, the effect of overlapping stents will be explored by looking at patients with single vs. multiple stents.

The results of all subgroup analyses will be presented in the final study report regardless of the findings. Descriptive statistics will be presented by subgroup including frequency and percent. The study is not powered for these subgroups, however, so these analyses are considered exploratory. While it is expected that some differences between these groups will exist, any statistically significant (at  $\alpha=0.15$ ) and/or clinically meaningful (or clinically unexpected) differences between subgroups will be reported along with the primary results. No formal statistical inference will be made within subgroups with respect to the performance goal for labeling purposes, only descriptive statistics will be presented. As no formal inference regarding subgroups will be made, no adjustment for multiplicity is indicated.

#### 9.2.8. Analysis Windows and Definitions

Study subjects are required to return for clinic visits post-procedure at Day 30 ( $\pm 7$  days), Month 12 (365 days  $\pm 30$  days), and Month 24 (730 days  $\pm 60$  days). A final study visit at Month 36 (1095 days  $\pm 60$  days) is required as well; however, this visit may be completed either as a clinic visit or telephone visit. For ascertainment of the primary endpoints, if the subject is known to be event free at at least the lower limit of the visit window, that subject will be considered event free for the analysis. Thus, if a subject misses the 30 day visit, but is determined to have been event free up to the 12 month visit, then that subject will be considered event free. If the subject has no data past the lower boundary of the visit window, their data will be considered missing.

For the purposes of these analyses, 12 months is defined as 365 days post procedure, and similarly 24 and 36 months are defined as 730 and 1095 days, respectively. Procedure is considered day 0 so that days from procedure is defined as (visit date – procedure date).

### 9.3. Patient Disposition, Demographics and Other Baseline Characteristics

A tabulation of patient disposition will be presented including number enrolled, number treated, and number of withdrawals, including reasons for withdrawal as documented on the case report form.

The demographics and medical history will be presented in tabular form for all subjects enrolled in this study (ITT analysis set). Means, standard deviations, and sample size will be used to summarize continuous characteristics such as age. Percentages, raw number of subjects exhibiting a characteristic, and sample size will be used to summarize categorical characteristics such as gender. Demographic and medical history data will be additionally tabulated for the mITT and PP analysis sets.

### 9.4. Primary Endpoint Analysis

Endpoints will be analyzed using the modified intention-to-treat analysis set as described below. The study will be considered successful if both primary safety and efficacy endpoints have been met. An additional supportive analysis will be conducted in the ITT analysis set for the primary safety and effectiveness endpoints.

#### 9.4.1. Primary safety endpoint:

The primary outcome measure for safety is the composite of MAE as adjudicated by the CEC including death, major amputation performed on the target limb or CDTLR through 30 days from procedure. The one-sided lower 97.5% Agresti-Coull confidence bound will be computed for the composite and compared to the safety performance goal of 88% for bare Nitinol stenting as defined by the VIVA Physicians Inc. [4]. The performance goal will have been met if the lower

bound is greater than 88%. This analysis will be conducted in the mITT analysis population. Only subjects with sufficient follow-up data will be included. That is, only subjects with ascertainment of status past the lower window for the 30-day visit (with any ascertainment of status post 23 days on study) and/or subjects who experienced an MAE at any time prior to and including 30 days will be considered eligible for this analysis. Any ascertainment of status post 23 days includes subjects who may have had missing safety status at 30 days, but are found to be free of MAE at a later out-of-window date. This subject will be considered MAE-free at 30 days. It is not expected that there will be notable loss to follow-up at this time point, however, if any loss to follow-up is present, sensitivity analyses for excluding these data will be conducted as described in Section 9.2.3 above.

#### 9.4.2. Primary effectiveness endpoint:

The primary outcome measure for effectiveness is primary stent patency rate at 12 months as defined in Section 6.2.2. The one-sided lower 97.5% Agresti-Coull confidence bound will be computed for patency and this lower bound will be compared to the effectiveness performance goal of 66% for bare Nitinol stenting as defined by the VIVA Physicians, Inc.[4]. The performance goal will be met if the lower bound is greater than 66%. The mITT analysis population will be used for this endpoint; however, only subjects with valid endpoint data without imputation will be included. This includes all subjects with imaging data qualifying as a 12 month visit and/or subjects without imaging data who experienced a CDTLR through 12 months (365 days). Additionally, if a subject is missing stent patency status at the 12 month visit window but is found to be patent at a later out-of-window date, the subject will be considered patent at 12 months. Sensitivity analyses for excluding missing data will be conducted as described in Section 9.2.3 above.

Both primary endpoints must be met in order to declare trial success.

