### 6.2.2. Primary Effectiveness Endpoint

The primary outcome measure for effectiveness in the MIMICS-2 Study is primary stent patency rate at 12 months.

Patency is defined as no significant reduction in luminal diameter (i.e., < 50% diameter stenosis) since the index procedure. Luminal diameter is the value determined by the independent core lab. Loss of primary stent patency is deemed when PSVR >2.0, or where angiography reveals >50% diameter stenosis, or where the subject undergoes CDTLR. When both imaging modalities are available, angiography takes precedence.

[REDACTED]

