### 6.2.3. Secondary Endpoints

1. Contribution of individual MAE rates for death, major amputation performed on the target limb and CDTLR to the overall MAE rate at 30 days.
2. Long-term safety assessment – overall MAE rate at Month 12 and contribution of individual event rates to the overall MAE.
3. Overall rate and incidence of type of serious adverse events from Day 0 through completion of Study follow-up at Month 36.
4. Technical success reported by the core lab as the percentage of treated lesions in which a final result of ≤50% residual diameter stenosis (in-stent) was achieved at index procedure.
5. Primary stent patency rate: determined at Months 12 and 24 using values of: PSVR >2.0; >2.4; >2.5; and >3.5, each to indicate loss of patency on duplex ultrasound or where angiography reveals >50% diameter stenosis or where the subject undergoes CDTLR. When both imaging modalities are available, angiography takes precedence.
6. Clinical outcome: comparison of Rutherford Clinical Category measured at Baseline, Day 30, Months 12 and 24. Worsening of Rutherford Clinical Category is defined as an increase by one or more categories compared to Baseline or unexpected major amputation of the target limb.

[REDACTED]

[REDACTED]

7. Clinical outcome: comparison of Six-Minute Walk Test measured at Baseline, Day 30, Months 12 and 24 (sub-group of investigational sites).
8. Functional outcome: comparison of the ankle brachial index (ABI) measurement at Baseline, within 30 days after index procedure, then at Months 12 and 24.
9. Functional outcome: comparison of the Walking Impairment Questionnaire at Baseline, within 30 days after index procedure, then at Months 12 and 24.
10. Stent integrity measured as freedom from stent fracture, defined as clear interruption of a stent strut observed in a minimum of two projections, determined by core lab examination of X-rays taken with the leg in extension at 12, 24 and 36 Months.

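### A target-limb amputee with neither a 12-month image nor a CDTLR drops out of the primary patency test as missing, which can bias the patency rate upward, probably by little

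*SAP*

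**What the plan says.** SAP section 9.4.2 tests 12-month patency in the mITT set, but "only subjects with valid endpoint data without imputation will be included". It then names the ways in:

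- An image: "This includes all subjects with imaging data qualifying as a 12 month visit".
- A re-treatment without an image: "subjects without imaging data who experienced a CDTLR through 12 months (365 days").
- A late image, for successes only: a subject with no status in the window who "is found to be patent at a later out-of-window date, the subject will be considered patent at 12 months".

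Section 6.2.2 lists the failure events: "Loss of primary stent patency is deemed when PSVR >2.0, or where angiography reveals >50% diameter stenosis, or where the subject undergoes CDTLR". Redacted text follows that definition. No visible text there or in 9.4.2 mentions amputation.

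Section 9.2.3 states: "For all primary, secondary and exploratory analyses, no imputation of missing data is planned". It provides a tipping-point analysis of the primary endpoints on the ITT set. Section 9.2.8 treats a subject with no data beyond the lower edge of the visit window as missing.

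Elsewhere the SAP does count target-limb amputation. The primary safety composite in 9.4.1 is described as "including death, major amputation performed on the target limb or CDTLR through 30 days from procedure", and 9.4.1 admits any subject with such an event whatever the later follow-up. MAE is also tabulated at Month 12 (9.5.1). In 6.2.3, Rutherford worsening is an "increase by one or more categories compared to Baseline or unexpected major amputation of the target limb".

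**The concern.** The SAP already accepts that a clinical event can settle patency without an image, because CDTLR does so. It has no matching rule for target-limb amputation, an event that can make later imaging of the treated segment impossible. A failure that was re-treated is counted. A failure that ended in limb loss, with no re-treatment and no qualifying image, is not.

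Whether the subject is missing may therefore depend on outcome. If some of these amputations reflect stent failure, leaving them out raises the patency rate in the test that, together with safety, decides trial success.

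**Working it through.** **Inputs (SAP 9.1, 9.2.8, 9.4.2).** Goal 66%; assumed patency 75%; one-sided 97.5% lower Agresti-Coull limit; 230 evaluable subjects for 85% power; enrollment stopped at 271.

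**Formula.** With x patent of n, z = 1.96 and z² = 3.84:

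- ñ = n + z²
- p̃ = (x + z²/2)/ñ
- lower limit = p̃ − z√[p̃(1 − p̃)/ñ]

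**1. The plan's own figure.**

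- x = 166, n = 230: ñ = 233.84, p̃ = 0.7181, standard error 0.0294, lower limit 66.04%. Pass.
- x = 165, n = 230: lower limit 65.59%. Fail.

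The rule at n = 230 is therefore at least 166 patent. Exact binomial power is P(X ≥ 166 | 230, 0.75) = 85.6%, and exact type I error is P(X ≥ 166 | 230, 0.66) = 2.7%. The SAP's 230 for 85% power is reproduced.

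**2. Add k excluded amputees as failures.** The numerator stays and the denominator becomes 230 + k.

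| Starting result | k | Count | Lower limit | Goal met |
|---|---|---|---|---|
| 166/230 (72.2%) | 0 | 166/230 | 66.04% | yes |
| | 1 | 166/231 | 65.73% | no |
| 172/230 (74.8%) | 8 | 172/238 | 66.25% | yes |
| | 9 | 172/239 | 65.95% | no |
| 173/230 (75.2%) | 10 | 173/240 | 66.08% | yes |
| | 11 | 173/241 | 65.78% | no |

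Since 75% of 230 is 172.5, the last two starting results bracket the planned rate. One subject reverses a result at the pass mark; 9 to 11 are needed near the planned rate.

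**3. Chance of passing at the boundary.** The SAP gives no amputation rate, so the rates r below are assumptions. Suppose true success is exactly 66% when these amputees count as failures, and that every one of them lacks both image and CDTLR. After exclusion the rate among those analyzed is 0.66/(1 − r), and the chance of passing is P(X ≥ 166 | 230, 0.66/(1 − r)).

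| r | Rate after exclusion | Chance of passing |
|---|---|---|
| 0 | 66.0% | 2.7% |
| 0.5% | 66.3% | 3.4% |
| 1% | 66.7% | 4.3% |
| 2% | 67.3% | 6.7% |

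**4. What the tipping-point analysis sees.** If exactly 230 of 271 are evaluable, 271 − 230 = 41 subjects (15.1%) are missing. An amputee is one of those 41 and, on the visible text, is not distinguished from a subject who merely missed a scan. The analysis varies the outcome of missing subjects as a group; the primary test still uses the reduced denominator.

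**The case against.** The strongest reply is that patency is a property of the vessel, while MAE and the Rutherford category measure safety and clinical status. An event may count in those without defining patency. Section 9.1 shows the performance goals divided the same way: limb amputation belongs to the safety goal, and the 66% goal rests on ultrasound. This stands to the extent that the SAP does not contradict itself. It does not close the gap, because the SAP already goes beyond the ultrasound definition by adding CDTLR.

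A reader might infer more than the document supports:

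- *That these subjects are known failures, or that leaving them out can only help the device.* Nothing in the SAP says their stents had failed. Eligible lesions lie at least 3 cm above the bottom of the femur, so an amputation below the knee need not prevent imaging.
- *That limb loss cannot count at all.* An amputee with a failing qualifying image or a CDTLR does count as a failure. The tipping-point analysis can include scenarios where missing subjects failed, and amputation is reported in MAE and in Rutherford worsening. None of these changes the success rule.
- *That the false-positive rate is inflated as in step 3.* Those figures set 66% under the revised endpoint. Under the endpoint as the SAP defines it, the error at n = 230 stays at 2.7%.

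Finally, the redacted text after the definition in 6.2.2 could hold a rule on this point. That cannot be judged from the visible document.

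**Conclusion.** The gap is real on the visible text. A subject with target-limb major amputation through day 365, no qualifying image (on time or late) and no CDTLR leaves both numerator and denominator of the primary patency test. Because amputation may prevent imaging and may reflect stent failure, the patency rate can be biased upward.

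The effect is probably small. Rutherford 5 and 6 are excluded at entry, so such events should be few, though the SAP gives no rate. The exclusion matters to trial success only for a result close to the pass mark. The conclusion assumes that the redacted part of 6.2.2 does not already classify these subjects. The rule should be set in advance, so that a known limb loss is not classified after the result is seen.

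**What to change.** First check the redacted text after the patency definition in 6.2.2. If no rule is there, add to 9.4.2:

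*A subject with CEC-adjudicated major amputation of the target limb through 365 days and no qualifying 12-month image is included as loss of primary patency. Where a qualifying image exists, the image decides.*

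- Day 365 matches the existing cut-off for CDTLR without imaging.
- Say whether a late image accepted under the existing out-of-window provision counts as qualifying, so that the two sentences do not conflict.
- Apply the same rule to patency at Month 24, through 730 days.
- Report a sensitivity analysis that excludes these subjects, which reproduces the present rule.

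The cost is a short addition to the SAP and one extra analysis. Target-limb major amputation is already adjudicated as an MAE component, so no new type of event has to be collected. The downside is that the patency rate may be slightly less favorable, and an amputation unrelated to the stent would count as a failure; the sensitivity analysis shows how much this matters.

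### The 12-month patency rule accepts images as proof of success to day 395 or later, but counts a re-treated subject without imaging as a failure only to day 365

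*SAP*

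**What the plan says.** Four SAP statements bear on when a stent counts as patent at 12 months.

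- **Entry to the analysis (9.4.2).** Two groups enter: "all subjects with imaging data qualifying as a 12 month visit", and "subjects without imaging data who experienced a CDTLR through 12 months (365 days").
- **Late images (9.4.2).** A subject with no patency status in the window who "is found to be patent at a later out-of-window date, the subject will be considered patent at 12 months". No latest day is given, nothing requires freedom from CDTLR before that image, and nothing is said about a late image showing loss of patency.
- **Windows (9.2.8).** The month-12 visit is day 365 plus or minus 30 days, so days 335 to 395. The same section says that "12 months is defined as 365 days post procedure". For both primary endpoints, a subject is event free if "known to be event free at at least the lower limit of the visit window".
- **Endpoint definition (6.2.2).** Patency is lost on PSVR above 2.0, on angiographic stenosis above 50%, "or where the subject undergoes CDTLR". No day limit is attached to the CDTLR. Section 9.4.2 refers to this definition.

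**The concern.** Evidence of success is accepted up to day 395, and without limit if it is favourable. For a subject without imaging, evidence of failure stops at day 365. Two kinds of subject fall into the gap:

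1. No qualifying image and a CDTLR on, say, day 380. Neither entry clause of 9.4.2 is met, so the subject can leave the denominator.
2. No in-window status, a CDTLR after day 365, then an image of an open lumen. The late-image sentence, taken literally, can score the re-treated stent as patent.

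The late-image sentence is also one-sided: a late patent image counts as success, while a late non-patent image has no stated use.

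Each gap moves the result towards the device, on the endpoint that sets the size of the trial and is judged against a fixed 66% goal.

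**Working it through.** **Inputs from the SAP.** Performance goal 66%, assumed patency 75%, one-sided 97.5% Agresti-Coull lower limit, 85% power and 230 evaluable subjects (9.1); month-12 window of days 335 to 395 and 12 months = day 365 (9.2.8). **Assumed input:** the share q of subjects affected. The SAP gives no CDTLR rate after day 365, so I show q = 1%, 2% and 3%.

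**Step 1: reproduce the plan's figure.** With x patent of n and z = 1.96, let ñ = n + z² and p̃ = (x + z²/2)/ñ. The lower limit is p̃ − z·√(p̃(1 − p̃)/ñ).

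For n = 230, ñ = 233.84.
- x = 165: p̃ = 0.7138, limit 65.6%, fails.
- x = 166: p̃ = 0.7181, limit 66.04%, passes.

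Success therefore needs at least 166 of 230 (72.2%). The exact binomial chance of reaching 166 is 0.856 at true patency 75% and 0.027 at 66%. The 230 reproduces, and this point does not affect it.

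**Step 2: sensitivity at the boundary.** Start from 165/230, which fails.
- One failure called patent gives 166/230: limit 66.04%, passes.
- Two failures dropped give 165/228: p̃ = 0.7200 with ñ = 231.84, limit 66.2%, passes.

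**Step 3: chance of a false pass.** Let true patency be exactly 66% when the affected subjects count as losses.
- Called patent: P(X ≥ 166), with X binomial (230, 0.66 + q).
- Dropped: K, binomial (230, q), subjects leave. The rest are patent with probability 0.66/(1 − q) and are tested against the threshold for 230 − K.

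| q | expected affected (230 × q) | all dropped | all called patent |
|---|---|---|---|
| 0 | 0 | 2.7% | 2.7% |
| 1% | 2.3 | 3.8% | 5.3% |
| 2% | 4.6 | 5.8% | 9.8% |
| 3% | 6.9 | 8.9% | 16.6% |

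Fixing the number dropped instead of letting it vary gives 7.9% at q = 3% (223 subjects remain and 162 must be patent). The other dropped entries are unchanged to one decimal.

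**Step 4: what the text gives for each case.**

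| Subject | Under 9.4.2 | Under 6.2.2 |
|---|---|---|
| No image, CDTLR by day 365 | Included as failure | Loss |
| No image, CDTLR on days 366–395 | Neither clause met; can be dropped | Loss, no day limit |
| No in-window status, CDTLR after day 365, later open image | Literally patent | Loss |
| No in-window status, later non-patent image | No rule | Loss, date of loss unknown |
| In-window image, then CDTLR by day 365 | Included; CDTLR not mentioned | Loss |

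The middle three rows need reconciling. The last is settled by 6.2.2, but the event-free rule in 9.2.8, which stops at day 335, blurs it.

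**The case against.** The other side has substantial points.

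- **A reader might infer that the SAP scores repaired stents as patent.** It does not say so. The day-365 limit is written only for subjects without imaging, and 9.4.2 takes its definition from 6.2.2, where patency runs from the index procedure and CDTLR is a loss. A sensible analyst would fail a re-treated stent. What stands is that the late-image sentence omits this condition, so the literal text allows the other result.
- **A CDTLR on day 380 is not a 12-month event if 12 months means day 365.** This is fair. But then an image from after day 365 should not establish patency unless the subject is free of CDTLR up to that image. The fault is the mismatch, whichever day is chosen.
- **Some of these subjects would be caught anyway.** A core-lab angiogram at re-treatment by day 395 showing more than 50% stenosis could qualify as imaging and count as loss. The SAP does not say whether such angiograms are read.
- **A reader might infer that days 366 to 395 are a busy interval, because the 12-month visit itself prompts re-treatment.** The SAP does not say so, and a subject re-treated for that reason would usually already have a qualifying image. The affected group is mainly those with missed or non-diagnostic scans.
- **Sensitivity analyses exist.** The ITT tipping-point analysis (9.2.3, Figure 1a) covers dropped subjects, but not a subject already classified as patent, and it does not change the success rule. The planned Kaplan-Meier figures for patency and CDTLR do not change it either.
- **A reader might extend the point to safety, since the event-free rule in 9.2.8 covers both endpoints.** Section 9.4.1 already counts any MAE up to and including day 30, so nothing needs changing there.

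**Conclusion.** The point holds as a mismatch of time limits that leaves a few subjects without a single answer, each time in the device's favour. Re-treated subjects *can* be dropped or called patent; the SAP does not establish that they will be.

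The size is unknown. The type I error figures are illustrative and rest on an assumed 1–3% share. The 5.3–16.6% series also needs every such subject to be scored patent against the definition in 6.2.2, so it is an upper case. The one-subject and two-subject flips apply only to a result sitting at the pass mark.

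The true share is probably small. The plan expects more than 230 of 271 subjects to be evaluable, so fewer than 41 (271 − 230) would lack status. Finding 2.3 to 6.9 dropped subjects among 41 would mean about 6% to 17% of them re-treated within one 30-day span.

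The rule still merits correcting, because it decides the primary endpoint and costs little to settle.

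**What to change.** Reconcile 6.2.2, 9.2.8 and 9.4.2 by adding to 9.4.2:

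> A CDTLR through the later of day 365 and the date of the qualifying image (through day 395 if there is no qualifying image) is loss of primary patency. An image obtained after a CDTLR cannot establish patency. Late out-of-window images are used by one stated rule, whether they show patency or loss of patency.

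The SAP should then state that late-image rule.

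In 9.2.8, add to the event-free rule, for effectiveness only, that no CDTLR is recorded through day 365.

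The cost is SAP wording. No new data are needed and the sample size does not change. The reported patency rate may become slightly less favourable.
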